8.8 Unscheduled Visit

Unscheduled visits may be performed anytime during the study to assess or monitor AEs, or at the subject's or Investigator's request. The date and reason for the unscheduled visit should be recorded in the source documents.

If unscheduled visits occur, the Investigator must record the following in the subject's source document and eCRF:

- Reason for unscheduled visit
- AEs or SAEs as per Section 11.1.2.
- Recording of any changes or additions to concomitant medications (dose or regimen)
- Any clinical assessments, vision- and non-vision-related, deemed appropriate for the clinical care of the subject.

Unscheduled visits should not alter the timing of the routine study schedule.

9. DESCRIPTION AND METHODS OF STUDY ASSESSMENTS AND PROCEDURES

9.1 Demographics, Medical History, and Prior Medications

The baseline demographic data of age and gender will be imported from the RESCUE or REVERSE clinical database into the long-term follow-up clinical database.

The medical history will be reviewed and updated by the Investigator or qualified designee.

All relevant prior medications will be recorded, including prescription and non-prescription medications, preparations and health and/or dietary supplements taken by the subject. Concomitant medications from the RESCUE and REVERSE studies may be recorded as prior medications with respect to the long-term follow-up study.

9.1.1 Physical Examination

Physical examination will be performed by the Investigator, or designee, and will include general appearance, skin, head, eyes, ears, nose, throat, neck, thyroid, chest/lungs, heart, abdomen, lymph nodes, extremities; and subject height and body weight.

All abnormalities should be clearly documented. A clinically significant abnormal finding that is causally related to the study medication or study procedure in the judgment of the Investigator will be recorded as an AE.

9.2 Vital Signs

Vital signs will be assessed and recorded at Visit 1 and Visit 5/EOS or ETV by the Investigator or designee and will include temperature, pulse rate, and systolic and diastolic blood pressure (after sitting at rest for 5 minutes). A clinically significant abnormal finding that is causally related to the study medication or study procedure in the judgment of the Investigator will be recorded as an AE.

9.3 Electrocardiogram

A 12-lead ECG will be recorded at Visit 1 and Visit 5/EOS or ETV by the Investigator as part of the general safety assessment and will include R-R interval, PR interval, QRS complex, and QT interval. The ECG should be recorded prior to blood collection and the subject will be in a supine position and at rest for at least 10 minutes prior to the start of the recording. The ECGs will be reviewed and read locally at the investigative center site to assess any abnormalities of which should be clearly documented. A clinically significant abnormal finding that is causally related to the study medication or study procedure in the judgment of the Investigator will be recorded as an AE.

9.4 Clinical Laboratory Testing

Venous blood samples will be taken for hematology and chemistry testing at Visit 1 and Visit 5 (EOS) or ETV. The following parameters will be determined:

- Hematology: complete blood count including red blood cells, hemoglobin, hematocrit, white blood cells with differential counts, and platelets.

- Serum chemistry: glucose, lipase, amylase, calcium, sodium, potassium, chloride, bicarbonate, blood urea nitrogen (BUN), and creatinine.
- Liver Function Tests: aspartate aminotransferase (AST), alanine aminotransferase (ALT), alkaline phosphatase (ALP), gamma-glutamyl transpeptidase (γ GT), total bilirubin, and albumin.

Analysis of samples will be conducted by the study central laboratory. Further details of the procedures to be followed for sample collection, storage, and shipment will be documented in a Laboratory Manual.

Additional and repeat laboratory safety testing may be performed at the discretion of the Investigator.

The Investigator, or designee, is responsible to review the results of all laboratory tests in a timely manner. For all abnormal values, the Investigator must provide comments on the laboratory results sheet, identifying those that are abnormal and clinically significant, as well as those that are abnormal and not clinically significant. A clinically significant abnormal finding that is causally related to the IMP will be reported as an AE as per the Investigator's judgment.

9.5 Quality-of-Life Assessments

QOL questionnaires will be administered in paper version at the study site. An interviewer will administer the questionnaire to the subject. The caregiver may be present but this is not required. QOL questionnaires must be performed prior to any vision or ocular testing.

9.5.1 36-Item Short Form Health Survey, Version 2

The SF-36 Questionnaire is a generic subject-reported outcome instrument used to assess QOL. It includes 36 questions that assess 8 health concepts:

- 1) limitations in physical activities because of health problems
- 2) limitations in social activities because of physical or emotional problems
- 3) limitations in usual role activities because of physical health problems
- 4) bodily pain
- 5) general mental health (psychological distress and well-being)
- 6) limitations in usual role activities because of emotional problems
- 7) vitality (energy and fatigue)
- 8) general health perceptions.

Each question has 5 answers scored 1 (unable to) to 5 (no difficulty). The scale score of each domain is calculated based on the summed score across items included in the domain, and is rescaled to 0 to 100 with higher scores indicating better health states (Ware 2007).

9.5.2 Visual Functioning Questionnaire-25

The VFQ-25 Questionnaire is a 25-item version of the 51-item Visual Function Questionnaire from the National Eye Institute. The VFQ-25 consists of 25 vision-targeted questions representing 11 vision-related constructs, plus an additional single-item general health rating question. All items are scored from 0 to 5, so that a higher number represents better functioning. To score the questionnaire, each item is converted to a 0-100 scale. Items within each subscale are averaged to create 12 subscale scores. The subscale scores (excluding the general health rating question) are then averaged to calculate the composite score.¹⁸

9.6 Ocular and Vision Assessments

The methodology for all the ophthalmic evaluations will be detailed in the standard operating procedures (SOPs) for ocular and vision testing. A central ophthalmology reading center will be used for quality control and analysis as detailed per evaluation in the study specific SOP. Ocular and vision assessments will be performed by the Investigator or other qualified site personnel.

9.6.1 Pelli-Robson Contrast Sensitivity

Contrast sensitivity will be measured using the Pelli-Robson chart.^{19,20} (Elliot 1990a, Elliott 1990b) The Pelli-Robson chart is comprised of eight rows of six optotypes of a constant size, with varying levels of contrast. The scoring will be based on the lowest contrast for which at least two letters in a triplet are reported correctly. The test will be administered at 1 meter. Assessment of the effect of GS010 will be analyzed.

9.6.2 Slit-Lamp Examination (Pre- and Post-Pupil Dilation)

Slit-lamp biomicroscopy examination will be performed per local standard medical examination techniques, pre- and post-pupil dilation, per the study schedule.

9.6.3 Goldmann Applanation Tonometry

Intraocular pressure will be measured per the study schedule by Goldmann applanation tonometry. Topical fluorescein and anesthetic will be utilized per standard local practices for the Goldmann applanation procedure.

9.6.4 Refraction for Best-Corrected Visual Acuity

Refraction will be performed as per the SOP for ocular and vision testing. Subject must be refracted prior to performing other vision assessments, for example visual acuity, contrast vision, and HVF testing. Refraction will be performed to obtain the BCVA for each eye.

9.6.5 Visual Acuity

Subjects will include both those with eyes able to read letters on the ETDRS chart, defined as on-chart eyes, and those with eyes unable to read letters on the ETDRS chart, defined as off-chart eyes. Please refer to the SOP for ocular and vision testing for the detailed definition of off- and on-chart eyes.

On-chart eyes will have an ETDRS score, as well as Snellen and LogMAR visual acuity values based on the letters/lines read on the ETDRS chart at 4- and 1-meter distances.

Off-chart eyes will not have an ETDRS score, Snellen or LogMAR visual acuity. Off-chart eyes will be tested for count fingers (CF) or hand motion (HM) visual acuity per the SOP for ocular and vision testing.

LogMAR visual acuity will be obtained for off-chart eyes based on the methodology described by Karanjia.²¹ (Refer to the SOP for ocular and vision testing for complete details). Briefly, the finger/hand dimensions of the examiner will be measured beforehand. The examiner will then present their fingers/hand to the subject to assess CF or HM vision, and will measure the distance at which the subject accurately counted fingers or detected HM. The finger/hand dimensions of the examiner and the distance at which CF or HM was performed will be entered into the equation,²¹ modified for assessment of visual acuity in meters. The output of interest is the LogMAR visual acuity.

For the purpose of the study, one ETDRS line will be considered equivalent to 0.1 LogMAR, and 1 ETDRS letter equivalent to 0.02 LogMAR.

9.6.6 Humphrey Visual Field 30-2

Standardized automated visual fields will be obtained with an HVF Analyzer II (Carl Zeiss Meditec Inc.) using the 30-2 SITA Fast test, Stimulus III White to measure mean deviations in decibels of sensitivity and other parameters obtained. A central reading center will perform quality control, analysis, and interpretation of all HVF results.

9.6.7 Spectral Domain Optical Coherence Tomography

SD-OCT will be assessed with the Spectralis® OCT (Heidelberg Engineering). Parameters will be obtained for the optic nerve (e.g., retinal nerve fiber layer [RNFL]) and posterior pole, per standard protocols included in the Spectralis software. A central reading center will perform quality control, analysis, and interpretation of all SD-OCT data.

9.6.8 Color Fundus Photos

Color fundus photos will be obtained at all visits and will be used for grading of vitreous haze. A central reading center will perform quality control, analysis, and interpretation of all color fundus photos.

10. SAFETY MEASUREMENTS AND VARIABLES

10.1 Adverse Events

10.1.1 Summary and Overview

An AE can be any unfavorable or unintended sign, including an abnormal laboratory finding, symptom or disease temporally associated with the IMP/study procedure, whether or not considered causally related with the IMP/study procedure.

Adverse events should be volunteered by the subject, be observed from examination of the subject at an investigative center visit, or from observations of clinically significant laboratory values or special examination abnormal values. AEs will not be solicited in this long-term follow-up study by the use of a specific list of anticipated events.

Surgical procedures planned before enrolment of the subject in the study are not considered AEs if the condition was known before study inclusion. In this case, the medical condition should be reported in the subject's medical history.

Worsening of visual acuity determined by the Investigator to be due to the progression of LHON will not be considered an AE.

10.1.2 Assessment and Documentation of Adverse Events

The Investigator will ask the subject at each follow-up visit how they have been doing since the last visit. The Investigator may inquire about any changes in their health status since the last visit and if the subject recalls and reports a health-related event to the Investigator, then the Investigator will use their medical judgment to determine whether the event is an AE. If the Investigator judges that the subject has had an adverse event, specific details will be explored for a complete AE assessment. If the subject is unable to recall specific details, the subject and/or Investigator may contact the subject's primary physician to collect the data needed for complete AE assessment. Further monitoring of AEs will occur for those AEs recorded on the eCRF.

AEs to be recorded on the eCRF and further monitored by the Investigator include the following:

- Any AE that is causally related to GS010 IVT and/or study procedure
- Any ocular or vision-related AE that is causally related or unrelated to study medication and/or study procedure
- Any SAE that is causally related or unrelated to study medication and/or study procedure.

Clinically significant abnormal findings observed during physical examination, vital signs measurement, or ECG recording will be recorded in the eCRF as an AE if the clinically significant abnormal finding is deemed as causally related to the study medication or study procedure.

Events are to be recorded by the Investigator or designee on the page titled “Adverse Events” of the eCRF (also called the “AE page”). The following AE data must be assessed and documented:

- Date of onset and date of resolution (i.e. actual dates when the event starts and is resolved rather than dates when the Investigator is informed).
- Nature/description of the event with self-explanatory and concise medical terminology (indicate a diagnosis or syndrome instead of symptoms). A diagnosis (a single diagnostic term), if available, should be used for documentation in the eCRF, rather than a subset of individual symptoms comprising the diagnosis; each diagnostic verbatim term will be counted as a single AE.
- Severity.
- Relationship to GS010 IVT injection.
- Relationship to study procedure.
- Seriousness.
- Any action taken regarding the event, whether by the Investigator, the subject (as reported by the subject), or by another physician (as reported by the subject or in the subject’s medical record).
- Outcome.

AEs requiring therapy must be treated with recognized standards of medical care to protect the health and well-being of the subject. Any treatment given will be reported on the page "Concomitant medication" of the CRF.

If known, the name of any disorder or illness should be recorded, in preference to the listing of individual signs or symptoms.

Severity Intensity/Grading

The severity of clinical AE is graded according to the Common Terminology Criteria for Adverse Events (CTCAE) version 4.0. The CTCAE scale will be provided to Investigators.

Should an event be missing in one of the scales, the following 3-point scale must be used:

- Mild: discomfort noticed, but no disruption of normal daily activity.
- Moderate: discomfort sufficient to affect normal daily activity.
- Severe: inability to work or perform normal daily activity.

Table 2 shows the correspondence between the severity levels of the CTCAE grades and the 3-point scale grades.

CTCAE	3-Point Scale
1	Mild
2	Moderate
3/4/5	Severe

CTCAE, Common Terminology Criteria for Adverse Events

Relationship to IMP and/or Study Procedure(s)

The Investigator is requested to assess the relationship of any clinical adverse experiences to study treatment and/or study procedures. The relationship of each AE to the study treatment and/or study procedures will be evaluated using the following definitions:

- Unrelated: There is evidence of relationship to a cause other than the GS010 IVT injection or study procedure. Does not meet criteria listed under unlikely, possible, or probable.
- Unlikely: Does not follow a reasonable temporal sequence from administration of GS010 IVT injection or study procedure and is most likely produced by the subject's clinical state and/or by environmental factors and/or by other therapies administered.
- Possible: Follows a reasonable temporal sequence from administration of GS010 IVT injection or study procedure and is not likely produced by the subject's clinical state and/or by environmental factors and/or other therapies administered.
- Probable: Follows a reasonable temporal sequence from administration GS010 IVT injection or study procedure. Clear-cut temporal association.
- Related: Includes all of the following:
 - It follows a reasonable temporal sequence from administration of the drug.
 - It could not be reasonably explained by the known characteristics of the subject's clinical state, environmental or toxic factors or other modes of therapy administered to the subject.
 - It follows a known pattern of response to the suspected drug.

Outcome

The outcome of each AE will be rated as follows:

- Recovered
- Not recovered
- Recovered with sequelae
- Fatal; This outcome is to be used only for an event leading to death. The outcome of all other events at the time of the death must be reported. The outcome of ongoing ones is reported as "not recovered".

- Unknown
- Worsening; This outcome is used when an AE worsens. The new status of the event is documented as another AE in the eCRF.

10.2 Serious Adverse Event Assessing and Recording

An SAE is any untoward medical occurrence or effect that fulfills the following criteria:

- Results in death;
- Is life-threatening;
- Requires hospitalization or prolongation of existing inpatient hospitalization;
- Results in persistent or significant disability or incapacity;
- Is a congenital abnormality/birth defect;
- Important medical events not captured by the above but which may, for example, require medical intervention to prevent one of the above criteria.

Definition of Serious Criteria

Life-threatening: an AE is life-threatening if the subject was at immediate risk of death from the event as it occurred (i.e., it does not include a reaction that might have caused death if it had occurred in a more serious form).

Hospitalization: AEs requiring hospitalization should be considered SAEs. Hospitalization for elective surgery for a pre-existing condition that has not worsened, or hospitalization for routine clinical procedures that are not the result of an AE need not be considered AEs or SAEs. Any untoward event occurring during the procedure must be reported as an AE, either 'serious' or 'non-serious' according to the usual criteria. In general, hospitalization signifies that the subject has been detained (usually involving at least an overnight stay) at the hospital or emergency ward for observation and/or treatment that would not have been appropriate in the physician's office or outpatient setting. When in doubt as to whether 'hospitalization' occurred or was necessary, the AE should be considered serious.

Disability/incapacitating: an AE is incapacitating or disabling if the experience results in a substantial and/or permanent disruption of the subject's ability to carry out normal life functions.

Events Not to Be Considered an SAE

Events associated with hospitalization for the following will not be considered as an SAE:

- Evaluation or treatment of a pre-existing condition and a non-exacerbating condition as long as the condition(s) associated with the hospitalization:
 - Existed prior to the subject's entry into the study and has been recorded in the subject's medical history as documented in the CRF (e.g., degenerative disease)
 - Has not worsened in severity or frequency following the subject's exposure to study medication
 - Has not required a change in treatment management following the subject's exposure to the study medication.

- Treatment that is elective or has been planned in advance for a pre-existing condition and non-exacerbating condition.

Serious Adverse Event Documentation and Reporting

Reporting requirements for SAEs will be managed on behalf of GenSight by a third-party vendor.

Any SAE occurring during the course of the study, i.e., between the ICF signature and the EOS visit, **MUST be reported** to the Sponsor or their representative as soon as it becomes known. The Investigator must complete and email or fax a "Serious Adverse Event Form" to the Sponsor or their designee within 24 hours of occurrence or knowledge of the event.

An Investigator's delegate may complete the SAE form; however, the Principal Investigator or delegate physician must sign it. The form can be sent to the Sponsor or their designee with the delegate's signature if the Principal Investigator/delegate physician's signature cannot be obtained within one working day. The Principal Investigator/delegate physician's signature must be obtained as soon as possible, as must his/her evaluation of the relationship to the IMP. The signed form must be emailed or faxed to the Sponsor or their designee immediately.

The SAE form must be completed in English.

The initial report should be promptly followed by detailed, written reports, which will include copies of hospital case reports, autopsy reports and other documents when requested and applicable.

The Sponsor or designee will assess initial and follow-up SAE reports from the site for expectedness, which will be determined based on the most recent edition of the Investigator's Brochure. Reports of Suspected Unexpected Serious Adverse Reactions will be expedited to the regulatory authorities as required per local regulations as an Investigational New Drug (IND) Safety Report within the required time frame.

The Sponsor or designee will be responsible for informing the institutional review board(s) (IRB)/independent ethics committee(s) (IEC) of SAEs as required. Correspondence with the IRB/IEC relating to the reporting of SAEs will be retained in the study file. The Investigator will receive a copy of all correspondence with the IRB/IEC and maintain in the site files.

10.3 Ocular Inflammation Events

Specific assessment and documentation of ocular inflammation will be of interest, as ocular inflammation is commonly reported with use of intravitreal AAV-based gene therapy and was a noted adverse side effect in preclinical studies, the Phase I/II, and initial Phase III clinical studies of the IMP GS010. Specifically, standardized schemes for assessing anatomic location, severity, and clinical evolution will be employed. Specific scales will be used for anterior uveitis (anterior chamber) and intermediate uveitis (vitreous).

The Standardization of Uveitis Nomenclature (SUN) Working Group provided standardized methods for (1) anatomic classification of uveitis (**Table 3**); (2) grading scheme for anterior chamber cells (**Table 4**); (3) grading scheme for anterior chamber flare (**Table 5**); and (4) activity of uveitis terminology (for clinical evolution)²² (**Table 6**).

The National Institutes of Health (NIH) Grading System for Vitreous Haze is provided in **Table 7**.

Investigators will grade cases of ocular inflammation according to these scales.

Grading of anterior vitreous cells will be performed based on the slit-lamp examination utilizing a 1 mm by 1 mm slit-lamp beam and the same grading scheme used for anterior chamber cells (**Table 4**).

Grading of vitreous haze will be performed in a standardized fashion by the central ophthalmology reading center, based on color fundus photos of the posterior pole. Baseline color fundus photos will be obtained at Visit 1 (long-term follow-up study) for all subjects and fundus photos will be obtained at each visit thereafter. The NIH grading system²³ will be used to grade the vitreous haze on the fundus photo. **Table 7** and photos will serve as the basis for vitreous haze grading.

Type	Primary Site of Inflammation ^a	Clinical Forms of Uveal Inflammation include:
Anterior uveitis	Anterior chamber	
 • Iritis • Iridocyclitis • Anterior cyclitis
Intermediate uveitis	Vitreous	
 • Pars planitis • Posterior cyclitis • Hyalitis
Posterior uveitis	Retina or choroid	
 • Focal, multifocal, or diffuse choroiditis • Chorioretinitis • Retinochoroiditis • Retinitis • Neuroretinitis
Panuveitis	Anterior chamber, vitreous, and retina or choroid	
 • Diffuse; all intraocular structures

SUN, Standardization of Uveitis Nomenclature
^aAs determined clinically. Adapted from the International Uveitis Study group anatomic classification.

Grade	Cells in Field ^a
0	<1
0.5+	1-5
1+	6-15
2+	16-25
3+	26-50
4+	>50

SUN, Standardization of Uveitis Nomenclature
^aField size is a 1 mm by 1 mm slit beam.

[figure not shown]
[figure not shown]

Grade	Description
0	None
1+	Faint
2+	Moderate (iris and lens details clear)
3+	Marked (iris and lens details hazy)
4+	Intense (fibrin or plastic aqueous)

SUN, Standardization of Uveitis Nomenclature

Term	Definition
Inactive	Grade 0 cells ^a
Worsening Activity	Two step increase in level of inflammation (eg, anterior chamber cells, vitreous haze) or increase from Grade 3+ to Grade 4+
Improved Activity	Two step decrease in level of inflammation (eg, anterior chamber cells, vitreous haze) or decrease to Grade 0
Remission	Inactive disease for ≥ 3 months after discontinuing treatments for eye disease

SUN, Standardization of Uveitis Nomenclature
^aApplies to anterior chamber inflammation.

Table 7: Vitreous Haze (National Institutes of Health)

Grade	Amount of Vitreous Flare/Haze	Illustration
0	No flare	
0.5+	Trace	
1+	Clear optic disc and vessels, hazy nerve fiber layer	
2+	Hazy optic disk and vessels	
3+	Optic disc visible	
4+	Optic disc not visible	
Quality Unsatisfactory	Photo quality inadequate for vitreous inflammation grading	
Not Performed	Photograph not performed	

Source: Nussenblatt RB et al. Ophthalmology. 1985;92:467-471.

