5.2.2 Risk Assessment

This study is not an interventional study and there are no risks from administration of any IMP or study procedure. The long-term follow-up study will assess the safety of gene therapy IMP GS010 that was administered in the RESCUE and REVERSE studies. The risks associated with gene therapy IMPs are as follows:

Risk of Immune Response: Although the eye is considered to be an immune-privileged site,¹³ an expected risk is potential immune responses to the capsid and transgene. Immune reactions against the newly introduced foreign protein or a T-cell response to the capsid could lower the therapeutic efficacy or cause local inflammation. Immune reactions against adenovirus-associated viral vector serotype 2 (AAV2/2) will be monitored throughout the study. The AAV2/2 used in this study has been studied and employed in other ophthalmologic clinical trials such as type 2 trials and to date no major health concerns, including immunologic or clinical, have been reported.¹⁴

Insertional Mutagenesis: Adeno-associated viruses (AAV) are non-integrative viruses. Studies performed in vivo with mouse liver suggest that AAV vectors integrate into the host genome; however no direct evidence of tumorigenesis due to AAV2/2 integration or other AAV serotypes has been observed in all preclinical studies and clinical trial data accumulated so far. This risk is considered as minimal.

Germ-line Transmission: Based on preclinical and clinical data, the risk of germ-line transmission is low. The probability that a recombination event could occur is very low.

Dissemination: The risk of vector shedding after in vivo gene therapy depends on the route of administration and the vector dose administered. An exhaustive report gathered the bio-distribution and shedding data from pre-clinical and clinical studies obtained for the HADV-5 and AAV2/2 vector.¹⁵ These studies conclude that the more compartments the viral vector has

to pass to reach a certain excretion route, the lower the risk of shedding is, due to either dilution of the viral vector, or degradation in case of passage through the stomach or interaction with the immune system. The possible consequence of leakage of the vector into the environment is expected to be low as shedding is minimal and transient. Nevertheless, recombination with endogenous pathogenic replication-competent adenovirus might occur, therefore leading to AAV2/2 replication.

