8.7.2 Exploratory safety analyses

In order to perform following analyses, a medical review will be done to review all ocular AEs and classify them as Intraocular inflammation AE / Elevation of IOP AE (including the following terms: IOP increase, intraocular hypertension).

Additional medical review will be performed to identify concomitant treatments categories:

- Local IOP lowering agent,
- Systemic IOP lowering agent,
- Combination local and systemic lowering agents
- Local (topical) Corticosteroid (CS),
- Systemic CS.
- Combination local (topical) and systemic CS

The following descriptions will be made for GS010 eyes, SHAM eyes and overall.

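### Vitreous haze is graded centrally at every visit and inflammation cases are graded on SUN scales, but no planned analysis summarises any of these grades

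*Protocol*

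**What the plan says.** **Collection.** Protocol 10.3 gives inflammation its own section: "Specific assessment and documentation of ocular inflammation will be of interest", because it was seen with GS010 in preclinical, Phase I/II and initial Phase III work. The section sets out SUN schemes for anatomic class, cells, flare and activity (Tables 3 to 6) and the NIH vitreous haze scale (Table 7). On who grades, it says "Investigators will grade cases of ocular inflammation according to these scales", and for haze "Grading of vitreous haze will be performed in a standardized fashion by the central ophthalmology reading center". Protocol 9.6.8 adds: "Color fundus photos will be obtained at all visits and will be used for grading of vitreous haze". Table 1 schedules the photographs at all five visits. For the haze reference point, Protocol 10.3 says "Baseline color fundus photos will be obtained at Visit 1 (long-term follow-up study) for all subjects".

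**Analysis.** Protocol 7.5.1 names adverse events (AEs) and serious AEs as the safety variables, and Protocol 11.5 contains no analysis of haze, cell, flare or activity grades. In the SAP, fundus photography appears only as a row of the schedule in Section 3.2. SAP 8.6.1 tabulates ocular AEs. SAP 8.5.2.6 summarises slit-lamp findings as normal or abnormal. SAP 8.7.2 adds an exploratory step in which "a medical review will be done to review all ocular AEs and classify them as Intraocular inflammation AE" or as an IOP elevation, followed by descriptions of the treatments given.

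**Immune monitoring.** Protocol 5.2.2 says "Immune reactions against adenovirus-associated viral vector serotype 2 (AAV2/2) will be monitored throughout the study". The laboratory plan in Protocol 9.4 is "Venous blood samples will be taken for hematology and chemistry testing at Visit 1 and Visit 5 (EOS) or ETV", with liver function tests included.

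**The concern.** The primary objective is long-term safety, and ocular inflammation is the ocular risk that the protocol describes in most detail. Each subject has one GS010 eye and one sham eye, so a centrally read haze grade for both eyes at each visit gives a within-subject comparison that does not depend on anyone reporting an event.

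AE reporting does not replace this. Protocol 10.1.1 says that AEs are not solicited from a list of anticipated events, and Protocol 10.1.2 leaves it to the investigator's judgment whether a finding is an AE. When one is recorded, its severity is graded by CTCAE or a 3-point scale, not by the SUN or NIH grades. Low-grade haze that is never called an AE would have no graded display in the report. A reader could then take the absence of reported events as absence of inflammation, although the study holds standardised readings that could confirm or contradict it.

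**Working it through.** No sample size, power or alpha figure bears on this point. The check traces each inflammation measure from collection to analysis.

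| Measure | Collected on whom | Scale | Planned summary of the grade |
|---|---|---|---|
| Vitreous haze, central reading | All subjects, all visits (Protocol 9.6.8, 10.3, Table 1) | NIH, 0 to 4+, six levels (Table 7) | None |
| Anterior chamber and anterior vitreous cells | Inflammation cases (Protocol 10.3) | SUN, 0 to 4+, six levels (Table 4) | None |
| Anterior chamber flare | Inflammation cases | SUN, 0 to 4+, five levels (Table 5) | None |
| Uveitis activity | Inflammation cases | SUN terms (Table 6) | None |

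**Count.** 5 visits x 2 eyes = 10 central haze readings per subject. This is an upper bound: missed visits, withdrawals and photographs that Table 7 would class as unsatisfactory or not performed all reduce it.

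**What the SAP reports instead.**

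1. Ocular AEs, related or not, by MedDRA system organ class and preferred term and by severity, for the GS010 eye, the sham eye and both eyes, with listings (SAP 8.6.1). The severity is the CTCAE or 3-point grade of Protocol 10.1.2.
2. Slit-lamp findings as normal or abnormal, before and after dilation, by anatomical location and eye treatment, at baseline and every follow-up visit (SAP 8.5.2.6). This does not depend on an AE report, but it carries no grade and is not the central haze reading.
3. For AEs classified as intraocular inflammation, eyes and events by corticosteroid category, including no treatment, and treatment duration (SAP 8.7.2.2).

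The list of changes in SAP 8.8 does not say that the grades will go unanalysed.

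**Consequence for the scales.** Table 6 defines worsening as a two-step rise in the level of inflammation, with haze as an example, or a rise from 3+ to 4+. None of the three displays carries a SUN or NIH grade, so none can show it.

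**Baseline.** SAP 5.2 defines baseline as the last value before injection in RESCUE or REVERSE, with no exception for haze. Protocol 10.3 places the haze baseline photograph at Visit 1, about two years after injection. Any haze shift table has to state which applies. The documents do not say whether pre-injection photographs were graded in the parent studies.

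**Immune readout.** Table 1 and Protocol 9.4 list hematology, serum chemistry and liver function at Visits 1 and 5. No antibody or cellular immune assay is listed.

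**The case against.** The strongest reply is that the SAP dropped nothing. The protocol's endpoints, safety variables and Section 11.5 plan no grade analysis, and Section 10.3 is about assessing and documenting events. That is correct. A reader might infer that the SAP breaks a commitment to analyse the grades; the documents do not support this, because the gap begins in the protocol. It remains a gap: the SAP does summarise IOP, slit-lamp results, laboratory values, vital signs and ECG, so safety reporting already goes beyond AEs and SAEs.

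Four other inferences are tempting and should not be drawn.

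- *That inflammation reporting rests on a late, sponsor-run re-sorting of AE terms.* The ocular AE tables are the main reporting and need no re-sorting; a uveitis or iritis term would appear there directly. The medical review in SAP 8.7.2 is an exploratory addition. The SAP gives no date for it and does not say who performs it.
- *That the review yields nothing beyond treatment tables.* Untreated inflammation has its own category, so events by eye can be counted.
- *That SUN grades exist for every eye at every visit.* The protocol specifies them for cases. Only haze photographs cover everyone at every visit.
- *That immune assays were promised and omitted.* The sentence in Protocol 5.2.2 names no assay, and clinical monitoring satisfies it. This is a point of wording, separate from the haze table.

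It can also be said that the documents do not show the grades to be in the analysis database. That stands, and is carried below as an assumption.

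**Conclusion.** The point holds in this form: the protocol requires central haze grades for all subjects at all visits and SUN grades for inflammation cases, and neither Protocol 11.5 nor the SAP summarises any of them. Up to 10 haze grades per subject have no planned use. Inflammation recorded as an AE will be reported by term, CTCAE severity and eye; haze not called an AE will not be reported by grade.

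The primary endpoint and the AE analysis are not invalidated. What is lost is a graded within-subject comparison, bearing on the primary objective, that does not depend on an investigator reporting an event. That makes this more than a missing detail, and it should be corrected.

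The conclusion assumes that the part of the SAP between the partial-date rules (5.5.2) and the analysis sets (6), which was not available in the text reviewed, contains no grade analysis; its position makes one unlikely. It also assumes that the grades were recorded as the protocol requires. The documents do not state whether the readers of fundus photographs in this study are masked to the treated eye, so a report of the comparison should say.

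**What to change.** Add two descriptive displays to SAP 8.6.

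1. **Central haze.** NIH grade by visit for GS010 and sham eyes, with ungradable and missing photographs shown as separate categories. At each visit, give the number of subjects whose GS010 eye is graded higher than, equal to, or lower than the sham eye. Add the shift from Visit 1, stated as the haze baseline and as an exception to SAP 5.2. A footnote should say that the shift cannot show haze already present at Visit 1; the by-visit and eye-to-eye displays cover that.
2. **Inflammation events.** For each recorded event, the maximum SUN cell grade and flare grade, by eye.

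As a secondary wording point, state in the SAP or the report that the immune monitoring of Protocol 5.2.2 is clinical and that no immune assay is scheduled. Placing this in the SAP or report means that the protocol text need not be changed.

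The cost is a small amount of extra tabulation, with no new procedure or reading, provided the grades required by the protocol are in the database. If they are not, or will not be analysed, SAP 8.8 should say so and give the reason.
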